6.7.2 Handling of withdrawals and losses to follow-up

Intention to Treat (ITT) will be used to statistically analyse the results if there is loss to follow up, or if there are any deviations from the original assigned groups.

6.7.3 Participant Replacement following withdrawal

Replacements will not be sought for participants who withdraw from the study, as attrition has been accounted for in our sample size calculations.

6.8 Expected Duration of Study

The expected study duration is eight months. Subject to ethics approval We anticipate recruitment of participants to commence in December 2020. In this case, the last participant will finish no later than July 2021.

- 1. Recruitment to be completed April 2021
- 2. ReST first group to be completed by May 2021
- 3. The usual care group to be completed by July 2021
- 4. All study data analysis to be completed by August 2021

In the event that ethical approval only allows us to start in February,

6.9 Ethics Approval

Ethics approval will be sought from the University of Sydney Human Research Ethics committee and Cerebral Palsy Alliance Ethics Committee in that order.

Page 15 of 21 The effectiveness of Rapid Syllable Transition Treatment in improving communication in children with cerebral palsy: A randomized controlled study

6.10 Modifications to the Protocol

Any modifications to this application will be submitted to each HREC before they are implemented and will be recorded in the clinical trials register (ANZCTR)

6.11 Protocol Violations

To minimise and prevent protocol violation, the following will occur: The written treatment protocol will include instructions on the delivery of ReST, data recording, and data storage.

Provision of adequate training of speech pathology students on the delivery of ReST. Regular and on-going supervision of the students and observation of their treatment sessions.

Procedure for recording treatment dosage and participant responses at each session. Procedure for recording participant behavior and engagement after each session. Procedure for logging all data recording and storing.

If a protocol violation occurs, the person responsible will inform the Principal Investigator (PI) or, in case of a student, their student supervisor within 24 hours. The PI or the student supervisor records the violation in the protocol violation form. A plan to rectify the violation will be decided between the person responsible for the violation, their supervisor where relevant, and the PI. This is also recorded in the protocol violation form.

6. 12 Participant reimbursement

There are no participant reimbursement or incentives.

6.13 Continuation of therapy

The trial will continue provided that no adverse/serious events occur until either of the following has been met: (i) a sufficient number of participants have been recruited, or (ii) the study period has ended.

6.14 Statistical analyses

Data analysis will utilize repeated measures ANOVA and Cohen's d effect sizes to compare the treatments over time.

Repeated measures ANOVA (2 groups x 6-time points) will be run for the primary and secondary outcome measures.

If there is any attrition, an intention-to-treat analysis will be conducted.

For statistically significant comparisons, Cohen's d effect sizes will be calculated (Cohen, 1988).

7. ETHICAL CONSIDERATIONS (see data, section 10 for privacy and confidentiality) 7.1 Potential Risks and Proposed Benefits

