6.3 Population / Sample size including power calculation

Sample size:

The sample size will be 20 children, 10 in each group.

Sample size calculation:

Sample size calculator used: https://www.ai-therapy.com/psychology-statistics/sample-size-calculator)

This pilot RCT is the first to use ReST with children with CP in a randomised controlled trial. There are no previous studies of this intervention with this population using the proposed outcome measures from which sample sizes could be calculated, so studies with similar populations, treatments, and measures were considered for sample size calculations. ReST is a motor speech intervention for the treatment of childhood apraxia of speech (CAS). While it has been shown to be effective in improving speech in children with CAS, it has not been researched with children with CP. Our exploratory pilot study on the use of ReST with children with CP indicated improvement in mean length of utterance, with a d2 effect size of 0.56. This effect size gives a sample size of 6. This was derived from calculating the effect sizes from the group means (baseline and maintenance), and standard deviation for four outcome measures. Speech MLU is a secondary outcome in the current study ReST effect sizes have primarily been calculated using d2. Using this metric, Thomas (2017) reported an average ReST intervention effect size of 5.55 (SD 2.41, range 2.48-8.52). (Previously published single-case clinician-delivered ReST treatment studies reporting similar dependent measures; McCabe et al., 2014; Thomas et al., 2014; Thomas et al., 2016). Using this effect size with a power of 0.8 and alpha of 0.05 the online sample size calculation produced a sample size of **3 for each group**. The only other RCT using ReST in children with CAS produced an effect size (Cohen's d) of 1.376 giving a sample size of 10 for each group.

The other motor speech interventions used with children with CP include LSVT LOUD (Boliek & Fox, 2017), Speech Systems Intelligibility Treatment (Pennington et al., 2010; 2013), and PROMPT (Ward, 2012). Sample size calculations were derived for each of these studies.

LSVT LOUD: Boliek & Fox, 2017 reported a Cohen's d effect size of 0.3 for pre and post speech intelligibility measures. The sample size calculation was therefore a sample size of 52.

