Speech Systems Intelligibility Treatment: Effect sizes were not reported in these studies, so they were calculated from the published study data. These were (Pennington et al., 2010) Cohen's d effect size of - 0.5 and (Pennington et al., 2013) 0.6 respectively. The sample size calculation was based on these provided sample sizes of 19 and 23 respectively.

PROMPT: Ward (2012) reported a Cohen's d effect size for the percentage of phonemes correct each of the four children. The mean of these was 1.1. The sample size calculation was therefore 7.

The sample size figures calculated from the non-ReST studies on children with CP were notably larger than those based on the ReST treatment studies. Although studies on children with CP may require a large sample size due to their heterogeneity, a sample size that is too large may be presumptuous at this stage as the effectiveness of ReST with children with Cerebral palsy is not known. Besides, the interventions in these studies differed quite significantly from ReST intervention, which may render the sample sizes improbable. In the absence of previous comparable studies on the effectiveness of ReST in children with CP, studies with other populations using ReST, studies with CP population using different interventions, and an exploratory study on ReST with CP population were considered in sample size calculations. Based on these, and our best estimate, a sample size of six per group was satisfactory. This was increased to ten per group to account for potential attrition and to reflect the calculation from Murray et al. (2015) study on the effectiveness of ReST.

Page 10 of 21 The effectiveness of Rapid Syllable Transition Treatment in improving communication in children with cerebral palsy: A randomized controlled study

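### Section 6.14 names Cohen's d with no small-sample correction; a between-group d reported for every comparison would run 4.4% too high at 10 per group and 8.4% at 6

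*Protocol*

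**What the plan says.** Protocol section 6.14 states: "Data analysis will utilize repeated measures ANOVA and Cohen's d effect sizes to compare the treatments over time". It names the measure a second time, citing its standard source, and there ties its calculation to comparisons that reach statistical significance. It mentions no small-sample correction and does not say which contrast or which SD enters d.

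The sample is small. Section 6.3 says "The sample size will be 20 children, 10 in each group". Before that figure was settled, the same section held that "a sample size of six per group was satisfactory" and then that "This was increased to ten per group to account for potential attrition". No dropout rate is given. Section 6.7.3 adds that "Replacements will not be sought for participants who withdraw from the study", so the analysed groups can fall below 10.

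Section 6.3 also shows how the team uses effect sizes. It calls the study a pilot RCT and reads sample sizes off the effect sizes of earlier studies. One of these is the earlier ReST trial in childhood apraxia of speech, which "produced an effect size (Cohen's d) of 1.376 giving a sample size of 10 for each group".

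**The concern.** Cohen's d divides a mean difference by an estimated SD. In small samples the reciprocal of that SD is too large on average, so d is biased away from zero. The size of the bias depends only on the degrees of freedom of the SD, and a known factor removes it; the corrected estimate is Hedges' g. With 18 degrees of freedom or fewer, the bias is visible in the second decimal place.

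The main consequence is for later planning. Section 6.3 sizes this trial from published d values, so the d reported here is a likely input to the next trial. Required sample size varies as 1/d², so an average overstatement of d carries through to a later trial that is somewhat too small. The direction also favours ReST.

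**Working it through.** **Inputs.** From section 6.3: 10 per group planned; 6 per group as the number before the increase; alpha 0.05 and power 0.80; d = 1.376 from the earlier ReST trial; 0.56 from the team's exploratory pilot. From section 6.14: Cohen's d as the measure. Assumed, because the protocol does not state them: two-sided testing, and a between-group d with one pooled SD, so df = 2n − 2.

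**The plan's own figure.** A two-sided two-sample t-test with d = 1.376, alpha 0.05 and power 0.80 needs n = 9.36, so 10 per group. This agrees with section 6.3. The protocol gives no figure for the bias of d.

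**Small-sample bias when every d is reported.** The mean of d is δ/J, where δ is the true effect and

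J(df) = Γ(df/2) / [√(df/2) × Γ((df − 1)/2)].

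| n per group | df | J | overstatement, 1/J − 1 | shortfall in a later n, 1 − J² |
|---|---|---|---|---|
| 10 | 18 | 0.9576 | 4.4% | 8.3% |
| 8 | 14 | 0.9453 | 5.8% | 10.6% |
| 6 | 10 | 0.9227 | 8.4% | 14.9% |

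In absolute terms:

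- True d 0.50 at 10 per group: mean reported d = 0.50/0.9576 = 0.522, a bias of about 0.02.
- True d 0.50 at 6 per group: 0.50/0.9227 = 0.542, a bias of about 0.04.
- True d 1.376 at 10 per group: 1.376 × 0.0442 = about 0.06.

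For scale, the usual approximation to the standard error of d at 10 per group and d = 0.50 is √(2/10 + 0.25/40) = √0.20625 = 0.45; the exact value is nearer 0.48. A bias of 0.02 is about 5% of one standard error.

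**The significance condition, for comparison.** At 10 per group, two-sided significance requires |d| of at least 2.101 × √(2/10) = 0.94. Simulation of 1,000,000 two-group comparisons per scenario gave these average overstatements:

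| True d (10 per group) | all comparisons | significant only | significant and positive, after multiplying by J |
|---|---|---|---|
| 1.376 | 4.4% | 15% | 11% |
| 1.0 | 4.4% | 39% | 33% |
| 0.8 | 4.4% | 65% | 58% |
| 0.56 | 4.4% | 122% | 114% |
| 0.50 | 4.4% | 145% | 137% |

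The "all comparisons" column is the exact value; the simulated values agree with it. The correction therefore does what it should only on an estimate that has not been selected for significance.

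**The case against.** The best case for leaving 6.14 alone has four parts.

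**Detail for an analysis plan.** The protocol never says that d is uncorrected, and the exact variant and the divisor are often left to an analysis plan, which is not shown here. This stands in part: a reader might infer that the protocol prescribes an uncorrected d, and the text does not go that far. What it does is choose a measure by name and source. The suggestion is to replace that choice with a better one, not to charge an omission.

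**Immateriality.** At the planned size the bias is small beside the sampling error. This stands and sets the rating.

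**Dependence on the divisor.** This stands too. A one-group change d at n = 10 (df = 9) would be 9.4% too high. An SD pooled over the 2 groups and 6 time points that 6.14 names would have up to 12 × 9 = 108 df, ignoring within-child correlation, and a bias under 1%. The 8.4% end also needs a loss of 4 in 10 children per group.

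**Comparability.** Earlier ReST work reports d. Printing both values meets this.

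Three stronger readings are tempting and are not supported:

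- That 4% to 8% is the overstatement whether or not results are filtered by significance. Under 6.14's own condition it is about 15% to 145% at 10 per group for true d between 1.376 and 0.50. The small-sample bias exists apart from the filter but does not describe its effect.
- That the range covers any group size up to 10. It has a floor at 6; at 5 per group the figure is 10.8%.
- That the reference to change over time implies division by the SD of change and hence a much larger d. The protocol names no such SD. The factor 1/√(2(1 − r)) depends on an assumed correlation r between visits: 1.58 at 0.8, 1.29 at 0.7, 1.0 at 0.5, and below 1 at lower values. It can go either way and is a separate matter from small-sample bias.

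**Conclusion.** The point holds as a minor one. Section 6.14 names Cohen's d alone, for a trial with at most 18 degrees of freedom between groups. On the assumptions of a between-group contrast, a pooled SD and reporting of every comparison, the average overstatement is 4.4% as planned and 8.4% at 6 per group. A later trial sized from that average d would be about 8% to 15% too small.

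This does not threaten the trial's conclusions. It is worth correcting because the direction is known and the remedy is nearly free. The larger weakness in the same section is that d is tied to significant comparisons, and replacing d by g without lifting that condition would leave most of the overstatement in place.

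**What to change.** In section 6.14, make Hedges' g (d multiplied by J) the reported effect size, with a 95% confidence interval, for the phase 1 difference between ReST and usual care. Name the visit, and divide by the pooled between-child SD at T1. The factor J still applies with that divisor: in simulation a mean d of 0.523 at 10 per group returned to the true 0.50.

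Report it for every outcome, whether or not the comparison is significant, because the correction does not work on an estimate filtered by significance. Print Cohen's d beside it so that results can be set against earlier ReST studies.

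The cost is a sentence or two in 6.14 and one multiplication per outcome. No data collection or design change is needed. The downside is that the reported effect is slightly smaller.

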6.2 Schedule of Events/ Treatment Phases

Table 1: Flowchart of the schedule of events

- 1. Rolling Recruitment: Please see section 6.4.1
- 2. Eligibility Screening: Participants will participate a screening assessment via teleconferencing. This will take 10 15 minutes.
- 3. **Baseline Assessment, T1**: All eligible participants will attend an initial assessment in person at the University speech pathology clinic or at the family's home. If this is not possible, the assessment will be conducted on teleconference.
- 4. The Consent form will be signed.
- 5. **Randomisation**: The children who are eligible to participate will be randomised to ReST first- group or usual care- group.
- 6. Treatment phase 1:
 - a. **ReST first- group:** Children in the treatment group will receive ReST therapy three times a week for six weeks, totalling 18 sessions.
 - b. Usual care- group: Children in the usual care group will continue their usual care therapy and complete T2 and T3 assessments. See Table 1, The Flowchart of the schedule of events. The content and dosage of usual care will be recorded. If the participant has a speech generating device, the frequency of use and device satisfaction will also be recorded.
- 7. **Treatment phase 1 Post intervention assessment, T2**: Within one week after the final ReST session.
- 8. **Treatment phase 1 Follow up assessment, T3:** Three weeks after the final ReST session.
- 9. Treatment phase 2:
 - a. **ReST first- group:** The children will complete T4 and T5 assessments.
 - b. **Usual care- group:** Children in the usual care group will commence ReST after T3 assessments are completed. See Table 1, The Flowchart of the schedule of events.
- 10. **Treatment phase 2 Post intervention assessment, T4**: Within one week after the final ReST session.
- 11. **Treatment phase 2 Follow up assessment, T5**: Three weeks after the final ReST session.

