6.4.5 Randomisation and Blinding Processes

Randomization

Participant randomization flowchart

After the Informed Consent Form is signed and the baseline assessment has been completed, an officer not connected with the study and at a separate location draws a concealed opaque envelope from a group of 20 identical envelopes. Each envelope contains the group allocation. The officer will inform the study coordinator who informs that family.

Children will be randomly allocated to one of;

1. A ReST first group who will receive ReST 3 days per week for 6 weeks, for a total of 18 sessions.

2. A usual care group who will receive usual care first and ReST after Treatment phase 1 Follow up assessment, T3 assessment.

Blinding

Blinding of the treating clinicians or the participants is not possible as this is a behavioural RCT. The treating clinicians are not able to deliver the intervention without knowing about it. The participants will not be blinded to the study treatment as they will know from recruitment that the treatment aims to improve speech. The clinicians scoring the assessments will be blinded to group allocation.

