7.1.2. Participant Benefits

The participants will not be disadvantaged by randomisation as both groups will receive the ReST intervention and all the assessments.

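### The only model in section 6.14 uses the pre-randomisation baseline T1 as a response level and does not adjust for it, so the phase 1 contrast is less efficient than it need be and moves with chance baseline imbalance

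*Protocol*

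**What the plan says.** The protocol places the baseline assessment before allocation. Section 6.2 says of T1: "All eligible participants will attend an initial assessment in person at the University speech pathology clinic or at the family's home", and lists randomisation as a later step. Section 6.4.5 confirms the order: "After the Informed Consent Form is signed and the baseline assessment has been completed, an officer not connected with the study" draws the envelope.

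Section 6.14 gives the purpose of the analysis, "Data analysis will utilize repeated measures ANOVA and Cohen's d effect sizes to compare the treatments over time", and then the model: "Repeated measures ANOVA (2 groups x 6-time points) will be run for the primary and secondary outcome measures". The factors are group and time. No baseline covariate, ANCOVA or baseline-constrained model appears anywhere in the protocol.

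Section 7.1.2 says that "both groups will receive the ReST intervention and all the assessments". Section 6.2 says "Children in the usual care group will commence ReST after T3 assessments are completed", so T2 and T3 are the only visits at which ReST is compared with usual care before the cross-over.

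**The concern.** Allocation cannot affect a score taken before it. T1 carries no information on the ReST effect, but it does predict a child's later scores. A good analysis uses it as a predictor. Section 6.14 does not say outright that T1 is a level of time, but its count of time points leaves no other reading. The schedule text names five assessments, T1 to T5, and neither six nor five levels can be filled without T1. (The mismatch between six and five is a separate matter.)

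With T1 as a response, the part of the group-by-time term that speaks to phase 1 compares T2 and T3 with T1 between groups. A change score subtracts the whole baseline difference, although only a fraction rho of it is expected to persist. The remainder is noise in the estimate. In a trial of 20 children allocated by a draw of envelopes, with no stratification described, sizeable chance differences at T1 will be common.

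**Working it through.** **Inputs.** From section 6.3: "The sample size will be 20 children, 10 in each group"; d = 1.376, the effect from the earlier ReST trial in childhood apraxia that gives 10 per group; and d = 1.1, the PROMPT figure. The same section states its targets as "with a power of 0.8 and alpha of 0.05". Sidedness is not stated, so two-sided is assumed. Rho is not in the documents; 0.3, 0.5 and 0.7 are shown. Also assumed: equal variances and equal correlations at all visits, d in units of the SD at one visit, and the same effect at T2 and T3.

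**The protocol's own figure.** A two-sample t-test with d = 1.376, power 0.80 and two-sided alpha 0.05 needs 9.36 per group, rounded up to 10. This reproduces. Power at 10 per group is 0.829.

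**Variance per child, in units of the outcome variance.**

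Single visit:
- change from T1: 2(1-rho)
- adjusted for T1: 1-rho²
- ratio, adjusted to change: (1+rho)/2, that is 0.65, 0.75 and 0.85 at rho 0.3, 0.5 and 0.7

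Mean of T2 and T3:
- change from T1: (1+rho)/2 + 1 - 2rho = 1.5(1-rho)
- adjusted for T1: (1+rho)/2 - rho²
- ratio: (1+2rho)/3, that is 0.53, 0.67 and 0.80

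The adjusted variance is then multiplied by 1 + 1/16 for estimating the slope with 20 children.

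**Power.** Non-central t with noncentrality d / sqrt(variance × 2/10), on 18 degrees of freedom for change and 17 for adjustment. For example, at rho 0.5 and d = 1.376 the T2-T3 mean gives 1.376/sqrt(0.75 × 0.2) = 3.55 for change and 1.376/sqrt(0.50 × 1.0625 × 0.2) = 4.22 adjusted.

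| | rho 0.3 | rho 0.5 | rho 0.7 |
|---|---|---|---|
| T2-T3 mean, d = 1.376: change | 0.81 | 0.92 | 0.99 |
| T2-T3 mean, d = 1.376: adjusted | 0.96 | 0.98 | 1.00 |
| T2-T3 mean, d = 1.1: change | 0.62 | 0.77 | 0.93 |
| T2-T3 mean, d = 1.1: adjusted | 0.85 | 0.89 | 0.96 |

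**Against the omnibus interaction.** This is the group-by-time F test over T1 to T5, with gains retained so that the groups no longer differ at T4 and T5. On 4 and 72 degrees of freedom at d = 1.376 its power is 0.895, 0.973 and 0.999 at rho 0.3, 0.5 and 0.7. The adjusted T2-T3 mean has 0.964, 0.978 and 0.997. The difference is about 7 points at rho 0.3 and practically nil from 0.5.

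**Chance imbalance.** The T1 difference between groups has SD sqrt(2/10) = 0.447 outcome SDs. P(|difference| > 0.5) = P(|Z| > 0.5/0.447) = 0.26. Given a T1 difference of 0.5 SD, the change contrast moves by -(1-rho) × 0.5, that is -0.25 SD at rho 0.5, -0.15 at 0.7 and -0.05 at 0.9. The adjusted estimate does not move.

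**The case against.** A repeated measures ANOVA with baseline as a level is a valid analysis. Its interaction contrast is unbiased over randomisations and already removes a constant offset between groups. The variance 2(1-rho) already contains the imbalance, so lost power and imbalance are one inefficiency seen from two sides. Rho is not documented. At d = 1.376 the change in the T2-T3 mean meets the 0.8 target at every rho shown, and covariates are often left to the statistical analysis plan. All of this stands except the last part: section 6.14 does not leave the model open but names an unadjusted one, and an analysis plan that adjusted for T1 would depart from it.

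Three stronger readings are tempting, and the documents do not support them.

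- A reader might infer that the ReST effect is tested by the group main effect, which would be diluted by T1. Section 6.14 speaks of comparing treatments over time, which points to the interaction. In a cross-over where both groups receive ReST, the group term compares sequences.
- A reader might infer that ANCOVA at T2 alone should replace the planned test. At d = 1.376 it has power 0.838, 0.901 and 0.976 at rho 0.3, 0.5 and 0.7, which is below the T1 to T5 interaction throughout. At rho 0.7 it is also slightly below the T1 to T3 interaction (0.734, 0.872 and 0.982).
- A reader might call the planned estimate biased. The shift is conditional on the imbalance that happens to occur.

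**Conclusion.** The point holds as one of efficiency and of robustness to chance imbalance. It does not make the planned analysis invalid. At d = 1.376, compared like for like on the T2-T3 mean, adjustment gains about 15 points of power at rho 0.3 and 6 at rho 0.5, and the gain is negligible from about 0.7. At d = 1.1 the gains are 23, 12 and 3 points. Against the T1 to T5 omnibus test the power gain is confined to low rho, but that test does not itself estimate ReST minus usual care in phase 1.

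These sizes rest on assumed correlations, compound symmetry and an equal effect at T2 and T3. The 26% figure depends only on 10 per group and an approximately normal T1 mean difference. Because the covariate is already collected and the loss from using it is at most trivial over the range shown, the change is worth making before data are analysed.

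**What to change.** In section 6.14, take T1 out of the response times. For the primary outcome, and for each secondary outcome measured at T1, estimate the phase 1 ReST minus usual care difference from a mixed model with T2 and T3 as responses and with group, visit, group-by-visit and the child's T1 score as terms. An ANCOVA on the T2-T3 mean is an acceptable alternative. Report the adjusted difference with its 95% CI. T4 and T5 can still be analysed separately for the second phase.

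The cost is a change of wording and one degree of freedom (17 in place of 18), already counted in the power figures. No new visits, data or children are needed.

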4. AIMS / OBJECTIVES / HYPOTHESES

Aim:

The study aims to investigate if Rapid Syllable Transition Treatment (ReST) is effective in improving speech intelligibility and communicative participation in children with cerebral palsy (CP).

Hypotheses:

- 1. ReST will be more effective in improving speech intelligibility in children with CP than usual care
- 2. ReST will be more effective in improving communicative participation in children with CP than usual care.

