6. STUDY DESIGN

6.1 Type of Study

This is a single blind cross-over randomised controlled trial. The children are randomised to the ReST group first or usual care first.

Page 7 of 21 The effectiveness of Rapid Syllable Transition Treatment in improving communication in children with cerebral palsy: A randomized controlled study

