6.5 Primary and Secondary Outcome Measures

The primary outcome measure:

Speech intelligibility. This refers to how easy it is to understand the child's speech. This is measured with:

- The Intelligibility in Context Scale (ICS; McLeod et al., 2012). ICS is an assessment to rate the intelligibility of children's speech in their daily environments.

- Word Intelligibility by Picture Identification (WIPI; Ross & Lerman, 1979). WIPI assesses the intelligibility of the child's speech in single words.

The secondary outcome measures:

1: Communicative participation - This is measured with:

- Focus On Communication Under Six assessment (FOCUS; Thomas-Stonell, et al., 2004). FOCUS is an assessment for parents to rate their perception of their child's communicative participation and confidence in everyday situations. Although FOCUS is designed for children aged 3-6 years, it is used in this study because there are no other assessment tools that measure communicative participation with older children. Previous studies in CP have reported the use of FOCUS with older children (Pennington, et. al., 2013).

- Speech Participation and Activity Assessment of Children (SPAAC; McLeod, 2004). SPAAC is a child-directed rating tool of participation levels for children with speech disorders.

2: Parent/ Carer and child satisfaction with participant's communicative participation. These are measured with:

-The Canadian Occupation Performance Measure (COPM; Law, et al., 2005). COPM is a goal-setting tool and an outcome measure. Participants are directed through a semi-structured interview to set intervention goals and to rate performance and satisfaction. This is done before and after the intervention.

Page 13 of 21 The effectiveness of Rapid Syllable Transition Treatment in improving communication in children with cerebral palsy: A randomized controlled study

3: Speech accuracy. This is measured with:

- Percentage of phonemes correct in word level. The percentage of phonemes correct (PPC) expresses the percentage of consonant sounds that are articulated correctly. It is considered a robust means of assessing articulation accuracy (Shriberg et al., 1997) and will allow comparison with previous ReST research.

4: Sentence complexity. - This is measured with:

- Mean length of utterance (MLU) in speech. Changes in the child's mean length of utterance, as measured by calculating the average number of morphemes in a child's utterances (Miller & Chapman, 1981).

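### The planned 2 x 6 repeated-measures ANOVA does not match the five scheduled assessments, and its omnibus tests do not isolate ReST versus usual care, which only T2 and T3 compare

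*Protocol*

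**What the plan says.** The main hypothesis in section 4 is directional and comparative: "ReST will be more effective in improving speech intelligibility in children with CP than usual care".

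Section 6.1 gives the design: "This is a single blind cross-over randomised controlled trial". Children are randomised to ReST first or usual care first. Section 6.2 lists T1 at baseline, T2 and T3 in phase 1, and T4 and T5 in phase 2. The usual-care group begins ReST once T3 is done. For the ReST-first group in phase 2 the entry is "The children will complete T4 and T5 assessments", with no further treatment listed. T2 and T4 are each set at "Within one week after the final ReST session"; T3 and T5 come three weeks after that session.

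Section 6.14 plans one analysis for every outcome: "Repeated measures ANOVA (2 groups x 6-time points) will be run for the primary and secondary outcome measures". It is paired with Cohen's d "effect sizes to compare the treatments over time", calculated for the statistically significant comparisons. No contrast, visit or period is singled out as the test of the hypothesis.

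**The concern.** There are two faults, one of count and one of question.

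The count: six time points are analysed but five are scheduled. Screening does not supply the sixth, because sections 6.2 and 6.4.4 use it only to settle eligibility and the Viking Speech Scale level.

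The question: the hypothesis is about ReST against usual care, and after T3 that comparison no longer exists between the randomised groups. A test that pools T1 to T5 can be diluted by visits at which both groups are treated, or can be significant because of them. With ReST justified by principles of motor learning (sections 3.1 and 3.2), retained gain is the hoped-for result, so dilution is what success would produce. At stake is whether a significant or non-significant omnibus result can be read as an answer to the hypothesis.

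A related weakness is that T2 and T3 are timed from a final ReST session, which usual-care children have not had in phase 1. The plan does not show how the one clean comparison is matched in time between groups.

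**Working it through.** **Inputs from the protocol.** 10 children per group; alpha 0.05; d = 1.376 behind the choice of 10 per group (section 6.3); visits T1 to T5 with crossover after T3 (section 6.2).

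**Assumptions, not in the protocol.** Two-sided tests; unit SD; equal correlation rho between visits, taken as 0.7 with 0.5 and 0.85 as the range; an illustrative d of 0.8.

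**1. Count.** T1, T2, T3, T4, T5 = 5, against 6 stated. With 20 children in two groups, the interaction has (5 − 1) = 4 and 18 x 4 = 72 df. Six time points would give 5 and 90.

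**2. The plan's own sample size.** A two-sided two-sample t-test with d = 1.376 and 10 per group has power 0.83, and 10 is the smallest n reaching 0.80. So the stated 10 per group reproduces, as a simple two-group comparison rather than a 2 x 6 ANOVA.

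**3. Group main effect.** Suppose ReST adds d.
- Gain retained: ReST-first means (0, d, d, d, d), average 0.8d; usual-care-first means (0, 0, 0, d, d), average 0.4d. Difference 0.4d, which is 0.55 when d = 1.376.
- Gain fades fully in the ReST-first group: (0, d, d, 0, 0) against (0, 0, 0, d, d). Both average 0.4d, so the difference is 0.

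**4. Group-by-time test.** Noncentrality = (n/2) x Σ(D_j − D̄)² / (1 − rho), where D_j is the group difference at visit j.
- Gain retained: D = (0, d, d, 0, 0), D̄ = 0.4d, and the sum is 2(0.6d)² + 3(0.4d)² = 1.2d². At d = 0.8 and rho = 0.7: 5 x 1.2 x 0.64 / 0.3 = 12.8.
- Groups differ only at T4 and T5, with no phase-1 difference: D = (0, 0, 0, −d, −d). The sum is again 1.2d² and the noncentrality again 12.8.
- Gain fades fully: D = (0, d, d, −d, −d), D̄ = 0, sum 4d², noncentrality 5 x 4 x 0.64 / 0.3 = 42.7.

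| Scenario, d = 0.8 | rho 0.5 | rho 0.7 | rho 0.85 |
|---|---|---|---|
| Interaction, difference at T2/T3 only | 0.55 | 0.80 | 0.99 |
| Interaction, difference at T4/T5 only | 0.55 | 0.80 | 0.99 |
| T1-adjusted mean of T2 and T3, difference at T2/T3 | 0.65 | 0.78 | 0.95 |
| T1-adjusted mean of T2 and T3, difference at T4/T5 only | about 0.05 | about 0.05 | about 0.05 |

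The first two rows come from the noncentral F distribution, the last two from simulation. The first two are identical because, under equal correlation, the test does not distinguish which two visits carry the difference. With full fading, interaction power exceeds 0.99 at rho 0.7.

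**5. Focused contrast.** The mean of T2 and T3 has variance (1 + rho)/2 and covariance rho with T1. The residual variance after adjusting for T1 is (1 + rho)/2 − rho², which is 0.85 − 0.49 = 0.36 at rho 0.7. T2 alone has residual variance 1 − rho² = 0.51 and, by simulation, power of about 0.62 at d = 0.8.

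**The case against.** The strongest reply is that comparing treatments over time most naturally means the group-by-time test, and that test performs well: about 0.80 power at d 0.8 and rho 0.7, and more if the gain fades. This stands. The fault is not low power. It also stands that if ReST and usual care were truly equivalent throughout, the groups would share one expected course and the interaction would reject at its nominal level, given its usual assumptions. The scenario with a difference only at T4 and T5 therefore shows that the test is non-specific; it is not a forecast of a likely false positive.

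A statistical analysis plan that is not shown may name follow-up contrasts. That is fair, but the six-versus-five conflict and the pooled ANOVA are fixed in the protocol itself.

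The Table 1 flowchart is not visible. The count rests on the numbered list in section 6.2, which ends at T5.

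A reader might go further in three ways that the protocol does not support:
- That the planned test has the low power of the group main effect. Section 6.14 does not designate the main effect as the test.
- That the effect would be halved by setting T2 against T4 within children. Section 6.1 uses the cross-over label, but section 6.14 plans no such contrast.
- That COPM is missing for usual-care children in phase 1. Section 6.5 says "This is done before and after the intervention" without restricting it to those times, and section 7.1.2 says "both groups will receive the ReST intervention and all the assessments".

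On timing, T2 and T3 are labelled as phase 1 assessments for the whole trial, so parallel timing may be intended. The wording does not secure it.

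**Conclusion.** The point holds in this form. Six time points conflict with five scheduled assessments, and none of the omnibus tests isolates ReST against usual care. The 0.4d dilution under full retention and the zero under full fading follow from the schedule alone, given an effect of equal size in both groups. The power figures depend on the assumed correlation, equal correlation between visits and d = 0.8. The interaction would probably detect a real ReST effect of that size at correlation 0.7 or above, but a significant result would show neither its direction nor whether it arose before or after the crossover. The main hypothesis needs both.

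**What to change.** In section 6.14, change six time points to five, or define the sixth assessment in section 6.2. State that the ReST-versus-usual-care conclusion rests on one pre-specified between-group contrast before crossover, adjusted for T1 and reported with a 95% CI. Use either T2 or the mean of T2 and T3. The repeated-measures model over all visits can remain as a description. T4 and T5 then give supportive evidence on retention and on the delayed group's within-group change.

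Reconcile the section 6.2 wording on T2 and T3 for children who have had no ReST in phase 1, so that the two groups' phase-1 assessments are matched in time. How to do so is for the sponsor; moving visits would be a schedule change, not just wording.

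The cost is mainly wording, and phase 2 becomes supportive. At d 0.8 and correlation 0.7 the mean of T2 and T3 has power of about 0.78 against 0.80 for the interaction. It gains at correlation 0.5 (0.65 against 0.55) and gives up a little at 0.85 (0.95 against 0.99). Choosing T2 alone costs more, at about 0.62 for correlation 0.7, which favours the mean unless T2 is the visit of main interest.
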